**PROTOCOL TEMPLATE INSTRUCTIONS HRP-503**

- These instructions accompany the MSSM “Template Protocol” document and are intended to assist you in developing a human research protocol.
- Using the MSSM “Template Protocol” document, prepare a document with the following sections.
- Note that, depending on the nature of your research, certain questions, directions, or entire sections below may not be applicable. Provide information if and when applicable, and in cases where an entire section is not applicable, indicate this by marking the section “N/A”. Do not delete any sections.
- **For any items below that are already described in the sponsor’s protocol, the investigator’s protocol, the grant application, or other source documents, you may simply reference the title and page numbers of these documents in the sections below, rather than cutting and pasting into this document.. Do NOT refer to any derived documents, such as the Sample Consent document, or other internal documents required with the submission.**
- When you write a protocol, keep an electronic copy. You will need to modify this copy when making changes.

**Brief Summary of Research (250-400 words):**

Fatigue is experienced much more frequently by individuals with traumatic brain injury (TBI) than in the general population and is relatively stable and persistent within one to two years of injury. The effects of post-TBI fatigue are considerable. Fatigue after TBI is strongly associated with depression, pain, sleep quality, self-reported neurobehavioral function (cognitive, motor, somatic), health related quality of life, and overall quality of life. Moreover there is evidence to suggest that post-TBI fatigue commonly goes untreated, due in part to the lack of validated treatment options.

	Protocol Name:	Management of post-TBI fatigue with light exposure
	Principal Investigator:	[name]., ABPP/Cn
	Primary Contact Name/Contact Info:	[name], [contact] , [name]
	Date Revised:	3/9/2016
	Study Number:	IF1813452

There are no empirically supported treatments for post-TBI fatigue although medications are routinely used in its treatment. Promising research from other disorders (e.g., cancer, chronic fatigue syndrome) and pilot research that we have conducted in individuals with TBI suggests that non-pharmacological approaches might be promising areas of study. Exposure to bright white light has been shown to reduce or prevent fatigue in women with breast cancer, people with seasonal affective disorder, and shift workers. It is a low cost treatment with minimal associated risks.

## 1) Objectives

- Aim 1: Evaluate the efficacy of 4 weeks of daily BWL exposure in reducing PTBIF immediately post-treatment and at one-month follow-up.
  - H1: Individuals receiving 4 weeks of daily BWL treatment will report significant reductions in fatigue compared to those receiving DRL
  - H2: Treatment effects will be maintained one month after treatment completion
- Aim 2: Explore potential effects of BWL exposure on mood, sleepiness, sleep quality, circadian rhythms, anxiety, cognition and life satisfaction.
  - H3: Individuals receiving 4 weeks of daily BWL treatment will report significant reductions in daytime sleepiness and depressed mood as well as improvements in sleep quality and circadian rhythms, compared to those receiving DRL
  - RQ1: Is treatment with BWL associated with improvements in anxiety, cognition and life satisfaction?
- Aim 3: Investigate potential mechanisms for effects of BWL exposure on fatigue, including changes in mood, sleepiness, sleep quality and circadian rhythms.
  - RQ2: Are treatment-related changes in fatigue mediated or moderated by mood, sleepiness, sleep quality and circadian rhythms?
- Aim 4: Determine whether individual characteristics are associated with treatment outcomes.
  - RQ3: Are demographic or other patient characteristics associated with positive treatment outcomes?

## 2) Background

Fatigue is a common problem after TBI that is related to, but distinct from, sleepiness, sleep difficulties and depressed mood. Fatigue affects up to 80% of individuals with TBI (far more than the general population) and is relatively stable and persistent after the first year post-injury. Post-TBI Fatigue (PTBIF) is strongly associated with depression, pain, poor sleep quality, neurobehavioral dysfunction and poor quality of life (QOL).

	Protocol Name:	Management of post-TBI fatigue with light exposure
	Principal Investigator:	[name]., ABPP/Cn
	Primary Contact Name/Contact Info:	[name], [contact] , [name]
	Date Revised:	3/9/2016
	Study Number:	IF1813452

To date, little evidence has been generated in support of treatments of PTBIF. Many medications including neurostimulants, dopaminergics, antidepressants and atomoxetine, as well as caffeine and herbal preparations, are used to manage fatigue or promote wakefulness, often with undesirable side effects. Only two controlled studies examining the efficacy of a pharmacological agent for PTBIF have been published. In a double blind, placebo-controlled crossover trial, Jha et al. randomized 53 individuals with TBI who complained of disabling fatigue and/or sleepiness to receive up to 400 mg of modafinil or placebo. Modafinil was not superior to placebo in treating either fatigue or sleepiness. Kaiser and colleagues conducted a double blind, placebo-controlled pilot study with 20 individuals with TBI and found that modafinil reduced daytime sleepiness, but did not reduce fatigue.

Behavioral management techniques, such as cognitive behavioral therapy (CBT), seek to reduce fatigue's effects through use of compensatory strategies, economizing energy use and improving sleep hygiene. These techniques are well-supported in conditions such as cancer and multiple sclerosis but have received little attention in the TBI literature, although Ouellet and Morin did demonstrate that CBT for post-TBI insomnia also improved fatigue. One randomized controlled study (RCT) of patients with TBI or stroke demonstrated significant improvements in mental fatigue and cognitive performance after 8 weeks of mindfulness-based stress reduction. Because data for the TBI group (n=11) were not analyzed separately, the effectiveness of this approach with TBI is not known.

Substantial evidence exists that aerobic exercise and other forms of physical activity reduce fatigue in individuals with cancer, multiple sclerosis and other conditions. Although there are studies currently underway at the NY-TBI-MS and elsewhere on the benefits of exercise after TBI, no research has yet been published.

Regular exposure to bright white light (BWL) is a new potential treatment for PTBIF. BWL treatment involves daily exposure to light (typically 30 minutes) using a small light box. Systematic reviews have shown that BWL is effective in reducing depression and in treating circadian rhythm disturbances and other sleep-related disorders. BWL has also been shown effective in treating sleep disorders in individuals with dementia and to reduce daytime sleepiness and improve cognitive performance in healthy adults without disabilities.

Although fatigue is commonly found in many medical disorders, the effect of BWL on fatigue in these populations has received little attention, with the exception of cancer-related fatigue (CRF). Liu et al. examined the relationship between ambient light exposure and CRF in 63 women with stage I-III breast cancer prior to and during chemotherapy. Fatigue was assessed using self-report, and light exposure was recorded with a wrist Actigraph (a watch-like device to monitor movement, activity and light levels). More light exposure was associated with less fatigue; changes in light

	Protocol Name:	Management of post-TBI fatigue with light exposure
	Principal Investigator:	[name]., ABPP/Cn
	Primary Contact Name/Contact Info:	[name], [contact] , [name]
	Date Revised:	3/9/2016
	Study Number:	IF1813452

exposure and in fatigue were also correlated.

Ancoli-Israel and colleagues reported on an RCT investigating the effects on CRF of daily exposure to BWL in 39 women diagnosed with breast cancer undergoing chemotherapy. Patients were assigned to receive either BWL or dim red light (DRL) for 30 minutes every morning throughout the first 4 cycles of chemotherapy (8-12 weeks) using a commercially available light box (Litebook®). In those receiving DRL, CRF increased significantly from baseline to the end of the last chemotherapy cycle. In contrast, subjects receiving BWL experienced no increase in fatigue. The DRL group also showed significant desynchronization of circadian rhythms compared to the BWL recipients. No adverse effects were reported in either group. This research suggests that BWL holds promise as a treatment for fatigue in other medical disorders, including TBI. Since TBI is associated with increased sleepiness, mood disturbance, poor sleep quality and disruptions of circadian rhythms, BWL therapy may also have beneficial effects in these domains and consequently result in improved cognition and life satisfaction.

While the mechanism by which light therapy affects fatigue is not well understood, it is thought to involve non-visual photoreception; i.e., action of light on the nervous system via the eye that is unrelated to vision. Rods and cones in the retina that convey visual information to the brain are most sensitive to green/green-yellow light (506 to 555 nanometers [nms]). Light-sensitive retinal ganglion cells produce melanopsin, a photopigment that is most sensitive to shorter wavelengths of light such as blue light (480 nms) but also responds to longer wavelengths. These ganglion cells project into various non-visual areas of the brain, including the suprachiasmatic nuclei in the hypothalamus, which regulate circadian rhythms and function as the body's internal clock. These cells also stimulate the pineal gland, which controls melatonin production. Via these channels, light exerts crucial alerting effects on the human brain, increasing serotonin levels and reducing melatonin production. Thus, several biological action mechanisms for light therapy on fatigue are possible, including increasing alertness and decreasing sleepiness, improving mood and sleep quality, and regulating circadian rhythms.

We have also conducted an *Intervention Development* study to examine the feasibility and safety of BWL treatment in individuals with PTBIF, to estimate effect size and assess sensitivity of measures. We randomized 13 individuals with PTBIF to receive 28 days of treatment with BWL or DRL. DRL is widely used as a placebo in light therapy studies because it is relatively inactive biologically, and is known to induce positive treatment expectations comparable to those of BWL, even though it is visibly different from BWL. Treatment involved sitting in front of the light box for 30 minutes per day within 30 minutes of waking. Actigraphy data and sleep diaries were collected for 3 days before and after treatment. Participants completed measures of fatigue, sleepiness, sleep quality, mood, treatment satisfaction, treatment credibility and outcome expectancy, before and directly after treatment and again one month after treatment.

	Protocol Name:	Management of post-TBI fatigue with light exposure
	Principal Investigator:	[name]., ABPP/Cn
	Primary Contact Name/Contact Info:	[name], [contact] , [name]
	Date Revised:	3/9/2016
	Study Number:	IF1813452

*Safety, feasibility and treatment compliance.* Side effects and adverse events were monitored weekly for all participants: none were reported in either treatment condition. All participants were able to use the light box independently at home. Some requested additional telephone guidance on the use and positioning of the light box; 8 of 12 reported “no difficulty” using the box and 4 experienced minor initial difficulties (e.g., angling it correctly). Daily reminders helped participants remember to complete their sleep diaries. Ten participants reported missing no treatment sessions; the other 2 reported missing 2 and 4 sessions each. One subject dropped out after one week of treatment saying that light box use conflicted with her schedule.

*Treatment credibility and satisfaction.* Treatment credibility measures were administered 1-2 weeks after starting treatment. Both treatments were found to be credible and subjects in both groups reported that they expected substantial symptom improvement. Satisfaction with treatment outcome was somewhat better in the BWL group.

*Treatment effects.* Change scores were used for between-group comparisons to remove effects of any baseline differences between groups. Robust effect sizes in Cohen’s “medium” and “large” ranges were seen for BWL both between and within groups (0.32-1.56) on fatigue measures (see Appendix VI for all effect sizes). In most cases, effects were somewhat decreased at follow up but were generally in the medium range. This is unexpected, as past research indicates that treatment effects dissipate after treatment is discontinued. Medium or larger effect sizes were also noted for BWL on measures of daytime sleepiness, sleep quality and mood. Effect sizes for DRL were generally small.

Actigraphy findings indicated improvements in sleep in both groups but with larger effect sizes for BWL. Circadian rhythm data were more ambiguous, with modest changes in phase and rhythmicity in both groups. These findings suggest that BWL and DRL therapy are safe, feasible and credible for use with individuals with TBI, that the measures selected were sensitive to treatment effects and that BWL may be a promising treatment for PTBIF, with potential benefits for daytime sleepiness, mood, circadian rhythms and sleep as well. Indeed, daytime sleepiness, mood, circadian rhythms, and sleep quality may actually function as mediators or moderators of BWL treatment effects on PTBIF, given their documented responsiveness to light exposure. Because of the promising initial findings in our small pilot study and the need for empirically validated PTBIF treatment, an *Intervention Efficacy* trial investigating the effect of BWL on PTBIF is warranted. Based on: 1] the literature on alerting effects and cognitive benefits of BWL and the connection between PTBIF and cognition; 2] our own unpublished research suggesting the important role of anxiety in PTBIF and sleep disturbance; and 3] potential improvements in life satisfaction resulting from BWL effects on function, we will evaluate cognition, anxiety and life satisfaction as potential secondary effects of treatment.

To date, no trials of BWL treatment have been conducted in individuals with TBI. However,

	Protocol Name:	Management of post-TBI fatigue with light exposure
	Principal Investigator:	[name]., ABPP/Cn
	Primary Contact Name/Contact Info:	[name], [contact] , [name]
	Date Revised:	3/9/2016
	Study Number:	IF1813452

research is under way in Australia examining the effects of blue light, with some positive preliminary results. We have chosen to examine the benefits of BWL rather than blue light in the proposed study for two reasons. First, evidence suggests that extended exposure to blue light may have harmful effects on the retina in older adults. Second, there is strong evidence that as people age, their circadian photoreception decreases, particularly for blue light. Using full spectrum BWL (400nm to 740nm) maximizes the potential benefits of light therapy in adults over 50, who represent a large and growing proportion of people with TBI. In the proposed study, we will examine the effects of age on therapy outcomes. Light therapy also has potential for PTBIF because of its low cost (less than \$200 for a Litebook), apparent lack of side effects and ease of access (it can be easily used at home without supervision), making it safer and more attractive for treating fatigue than pharmacological treatments.

### 3) Setting of the Human Research

All research procedures will be conducted in the Brain Injury Research Center at the Mount Sinai Medical Center at [name] and at the Centre for Neuro Skills facilities (all sites). Light box treatment will be self-administered in participants' homes.

### 4) Resources Available to Conduct the Human Research

This research capitalizes upon the existing infrastructure of the Mount Sinai Brain Injury Research Center (MS-BIRC) and the New York TBI Model System (NY-TBI-MS, #02-0677 P1) as it builds on a successful set of standard operating procedures for identifying and enrolling individuals with TBI into research projects, collecting clinical data and prospectively following patients with TBI. Our research team (which consists of four senior PhD level investigators, a PhD level statistician, one Masters level clinical research coordinator, and three research assistants with Bachelor's degrees in related fields, in addition to four postdoctoral research fellows with PhD or PsyD degrees in clinical psychology) has also developed expertise and standardized methods for collecting data from informants of patients who are enrolled in prospective longitudinal studies. Our research team collectively has conducted over a dozen clinical trials, published over 200 peer-reviewed manuscripts, and made presentations at over 100 national and international professional meetings. The research team for this particular study will be trained in the protocol and closely supervised by [name], an established researcher and licensed clinical neuropsychologist. Staff at the BIRC-MS will train the co-investigator and research coordinator at the Centre for Neuro Skills via conference calls, voice and video over internet protocols (such as Skype and Go To Meeting), and in-person meetings at either the Centre for Neuroskills or the BIRC-MS.

[name], Ph.D. is co-investigator and lead for the project at all Centre for Neuroskills sites involved (Bakersfield, CA, Los Angeles, CA, and in Dallas, TX) with the help of the onsite research coordinators. She is the Senior Neuroscientist/Research Coordinator at the Centre for Neuro Skills in Bakersfield, CA as of 2005. She has worked in TBI research for twelve years dating back to her

	Protocol Name:	Management of post-TBI fatigue with light exposure
	Principal Investigator:	[name]., ABPP/Cn
	Primary Contact Name/Contact Info:	[name], [contact] , [name]
	Date Revised:	3/9/2016
	Study Number:	IF1813452

Master’s thesis, with multiple journal publications and presentations. BIRC-MS Faculty, particularly [name], will provide consultation and oversight for this project as needed.

Clinical Research Coordinators will complete screening evaluations and consenting, as well as all assessments, training in use of light boxes, treatment adherence activities and basic data management. CRCs will be at minimum Bachelor’s level prepared, with experience in conducting clinical research and in working with individuals with brain injuries or related disabilities. The study PI will train CRCs to administer the assessments. CRC Level II will assist CRCs as needed, to ensure sufficient personnel for blinded outcome assessment and will train them for data management.

**5) Study Design**

**a) Recruitment Methods**

We will use recruitment techniques that have proved successful in our research, including flyers and discussions with our patients with PTBIF. We will distribute recruitment materials to individuals who participate in other studies or who attend support groups at our center, at consumer conferences and to previous research participants who have expressed willingness to be contacted for future studies. We will post information about the study on the MSMC and Mount Sinai Brain Injury Research Center websites and Facebook page, on Brain Injury Association websites and on clinicaltrials.gov. We will also contact patients seen by our collaborating physiatrists using post mail. Additionally we will distribute recruitment materials at other medical centers serving patients with TBI, such as NYU Langone Medical Center, through collaborating psychologists with patients appropriate for research. Our prior recruitment experience suggests that the sample will be diverse in terms of demographics and injury-based characteristics.

Additionally, we have added the Centre for Neuro Skills facilities, post-acute rehabilitation centers in Bakersfield, CA, Los Angeles, CA, and Dallas, TX as external sites for this project. The site expects to add 30-40 participants per year to the protocol. Patients undergoing post-acute rehabilitation at the Centre for Neuro Skills will be approached for participation in the study.

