**b) Inclusion and Exclusion Criteria**

Inclusion Criteria:

1. Documented TBI of any severity
2. At least 12 months post injury (PTBIF typically stabilizes by 12 months)
3. Presence of clinically significant fatigue, operationalized as a score of 22 or more on the Multidimensional Assessment of Fatigue (an empirically based cut point previously used for clinical fatigue in TBI);

	Protocol Name:	Management of post-TBI fatigue with light exposure
	Principal Investigator:	[name]., ABPP/Cn
	Primary Contact Name/Contact Info:	[name], [contact] , [name]
	Date Revised:	3/9/2016
	Study Number:	IF1813452

4. Age 18 or older
5. English speaking

Exclusion Criteria:

1. Neurological disease other than TBI
2. Pregnancy (because of pregnancy fatigue)
3. Medical illness causing fatigue, such as anemia, hypothyroidism, HIV, renal failure, cirrhosis or cancer treatment in the past year
4. Current major depressive episode or substance abuse
5. Diagnosed sleep disorder or high risk for sleep apnea
6. History of bipolar disorder or manic or hypomanic episodes
7. Current chronic, severe headaches
8. Sensitivity to bright light
9. History of retinal damage or disease.

**6) (NOTE: You may not include members of vulnerable populations as subjects in your research unless you indicate this in your inclusion criteria.)**

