After one month of light treatment (T2), we will re-administer the baseline battery along with satisfaction and user experience questionnaires and 3 more days of Actigraphy. One month after T2, we will administer the assessment battery a third and final time (T3). Research team members who conduct outcome assessments will be blind to participants' treatment allocations. They will enter the data only after the participants have completed all study assessments (i.e. after T3) to avoid bias. Participants will be asked not to reveal treatment allocation to research team members. Participants will also be asked to refrain from light treatment in the month intervening between T2 and T3. Upon completion of follow-up, interested participants will be offered a discount coupon to purchase their own light box if they wish to do so.

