**Study Monitoring and Safety**

Bright light therapy has an excellent safety profile and has been shown to be well tolerated by most patients. Side effects are infrequent; the most common ones are mild headache, eyestrain, nausea and agitation. Side effects generally remit spontaneously. Study exclusion criteria were chosen to maximize safety. We will ask subjects to inform us of any new or intensified symptoms or health problems that they experience while using the light box. If significant adverse effects are experienced, the participant will be directed to discontinue treatment temporarily and consult their physician. Subjects will be withdrawn from the study if they experience any clinically significant side effects beyond those anticipated or if side effects are severe. We will ask participants not to alter medication use during the study unless it is medically necessary, and to notify the research team if alterations are made.

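### Pilot participants and other light-therapy users are not excluded, and the request to avoid light treatment misses the T1-T2 period on which H1 rests

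*Combined protocol and SAP*

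**What the plan says.** **Recruitment.** Among many channels, section 5a names two that reach people with research experience: "We will distribute recruitment materials to individuals who participate in other studies", and material also goes "to previous research participants who have expressed willingness to be contacted for future studies". No type of earlier study is set apart.

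**The pilot.** Section 2 (Background) describes the team's own earlier study: "We randomized 13 individuals with PTBIF to receive 28 days of treatment with BWL or DRL". It relies on DRL as a placebo because it raises comparable expectations, "even though it is visibly different from BWL".

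**Eligibility.** Of the nine exclusion criteria, only two concern light or the eye: "Sensitivity to bright light" and retinal damage or disease. Neither pilot participation nor light therapy appears. The fatigue criterion is "Presence of clinically significant fatigue, operationalized as a score of 22 or more on the Multidimensional Assessment of Fatigue".

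**Restrictions during the study.** Under Enrollment and Assessments: "Participants will also be asked to refrain from light treatment in the month intervening between T2 and T3". The only other restriction of this kind concerns drugs (Study Monitoring and Safety): "We will ask participants not to alter medication use during the study unless it is medically necessary".

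**What H1 uses.** Section 6e powers the trial on a pre-post design. Section 6c brings in T3 data only when it extends the H1 model to ask whether effects last.

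**The concern.** The plan already treats outside light as a threat, since it asks participants to avoid it after T2. The request does not reach the four treatment weeks, and those supply the H1 contrast. Two gaps follow.

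- **Blinding.** The boxes look alike, but the light they emit does not. Participant blinding therefore rests on people not knowing which colour is thought to be active. A still-fatigued pilot participant meets the written criteria. That person has already used one colour for 28 days and may now be given the other. Fatigue is self-reported, so what the participant believes can move the outcome.
- **Contamination.** A DRL participant who owns or buys a bright light box may use it between T1 and T2 without breaking any rule. The Background section says such a device costs under $200 and can be used at home unsupervised, so this is plausible at every site, whether or not anyone returns from the pilot.

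At stake are the credibility of the placebo comparison and some of the power for H1.

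**Working it through.** **Step 1: reproduce the plan's figures.** Inputs from section 6e: 40 per arm, N = 80, alpha 5%, effect sizes 0.37 (treatment) and 0.32 (treatment by time). Read the effect size as Cohen's f and use a noncentral F with 1 and N − 2 = 78 degrees of freedom and noncentrality N × f².

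- Treatment: 80 × 0.37² = 10.95, power 90.5% (plan: 90%).
- Interaction: 80 × 0.32² = 8.19, power 80.7% (plan: 81%).

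Both agree. Reading the effect sizes as Cohen's d would give 38.0% and 29.8% (normal approximation), so f is the reading intended. The recruitment figures in the Number of Subjects section also agree: 80/0.85 = 94.1, so 95 enrolled; 95/0.70 = 135.7, so 136 screened.

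**Step 2: ceiling on pilot returners.** 13/95 = 13.7% of those enrolled. This is an upper bound. It needs all 13 to have agreed to be contacted, come back, and met every criterion.

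**Step 3: outside light in the DRL arm.** Let a share q of that arm receive light equivalent to BWL. The DRL mean then moves a fraction q of the way towards the BWL mean, and f becomes f × (1 − q), with the within-arm SD taken as unchanged. The documents give no value for q, so the values below are assumed.

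| q | f, treatment | Power | f, interaction | Power | N to restore power |
|---|---|---|---|---|---|
| 0 | 0.370 | 90.5% | 0.320 | 80.7% | 80 |
| 5% | 0.351 | 87.4% | 0.304 | 76.6% | 90 |
| 10% | 0.333 | 83.7% | 0.288 | 72.0% | 100 |
| 20% | 0.296 | 74.4% | 0.256 | 61.8% | 124 |

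For example, at q = 10% the interaction noncentrality is 80 × 0.288² = 6.64, against 8.19 in the plan.

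**Step 4: carry-over in returners.** Suppose k of the 95 enrolled are returners in whom the two lights no longer differ (assumed). Then f becomes f × (1 − k/95), and interaction power is 78.2% for k = 3, 75.4% for k = 6, and 68.4% for k = 13, the extreme case.

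**Step 5: unblinding.** No figure can be derived. Under fresh 1:1 allocation about half of any returners would get the colour they had before and half the other colour. A former BWL user who is still fatigued may expect less from BWL, and a former DRL user may expect more. The documents fix neither sign nor size.

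**The case against.** The case for leaving the plan alone has real substance.

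- **Re-enrolment is an inference.** Nothing says that pilot participants are on the contact list or will be enrolled. The list is one channel among many, and the added rehabilitation sites expect 30 to 40 participants a year from their own patients. This stands, and the true number may be close to zero.
- **Carry-over and outside light mainly dilute.** Randomisation balances prior exposure in expectation, H1 concerns change from a measured baseline, and the fatigue threshold removes people who are still well after the pilot. Section 2 also reports that past research saw effects fade once treatment stopped, although the pilot's own effects were generally still medium at one month. This stands: these routes cost power and do not by themselves favour BWL. But randomisation at baseline does not control light used afterwards.
- **Some safeguards exist.** Excluding a current major depressive episode and diagnosed sleep disorders removes many likely light-therapy users. Treatment credibility and expectancy are assessed a week into treatment, so a difference between arms could be seen, though section 6 gives that measure no named role. The discount coupon for a light box comes only after follow-up.
- **Covariate adjustment.** Section 6b adjusts for baseline imbalances, but only in variables that are collected. The text does not itemise the T1 battery, so prior light use may or may not be recorded.

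A reader might infer more than the documents support:

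- *That H1 is biased towards BWL by a calculable amount.* Any such figure would have to assume that every returner's report shifts in BWL's favour.
- *That the trial is not independent of its pilot.* Using pilot effect sizes for planning does not bias the result. Returners would be newly randomised with new data, and no pilot outcomes are pooled.
- *That a dose-effect claim is undermined.* The plan makes none.

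**Conclusion.** The gap is real and of minor to moderate weight. The eligibility criteria and the request to avoid light treatment leave the T1-T2 comparison open in two ways: weaker blinding if pilot participants return (at most 13.7% of those enrolled, direction of effect unknown), and dilution if DRL participants use their own bright light. Under an assumed 5% to 10% of the DRL arm with fully equivalent exposure, interaction power falls from about 81% to about 77% or 72%; partial exposure would cost less. The frequency of either route is not in the documents and is probably small. No stated figure in the plan is wrong.

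**What to change.** 1. In the Inclusion and Exclusion Criteria, make people randomised in the pilot light study ineligible.
2. Reconcile the request under Enrollment and Assessments with the H1 window, so that it also addresses light treatment other than the assigned box between T1 and T2. Any look-back period before T1, and any rule on clinically indicated light therapy, is for the investigators to set.
3. Record prior light therapy at T1 and outside light-box use at T2 and T3.
4. In section 6c, add a sensitivity analysis of H1 without prior or concurrent users, keeping the intention-to-treat analysis primary. Removing prior users conditions on a baseline fact. Removing concurrent users conditions on behaviour after randomisation, so that part is supportive only.

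The cost is at most 13 potential recruits, a few added questions and one further model. The targets of 80 completers, 95 enrolled and 136 screened need not change if those excluded are replaced.
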